8.2 Efficacy Analyses

8.2.1 Analyses of Primary Efficacy Endpoints

- Change from baseline in CSF heparan sulfate levels after treatment at Month 1, 6, 12
- Change from baseline in liver and/or spleen volumes after treatment, as measured by MRI at Month 1, 6, 12

Descriptive statistics (N, mean, SD, SE, median, MIN, and MAX) will be calculated at baseline and each post-baseline time point for observed values and change from baseline.

8.2.2 Analyses of Secondary Efficacy Endpoints

- Change from baseline in plasma or urine glycosaminoglycans or heparan sulfate after treatment at Month 1, 6, 12
- Change from baseline in CSF or plasma or leukocyte SGSH enzyme activity levels after treatment at Month 1, 6, 12
- Change from baseline in brain volumes after treatment, as measured by MRI at Month 12
- Change from baseline in sleep pattern as measured by the modified CSHQ at Month 6, 12
- Change from baseline in PedsQLTM Core Generic Scales total score at Month 6, 12
- Change from baseline in parent quality of life, using the PSI-4 at Month 6, 12

[figure not shown]
- Change from baseline in gastrointestinal symptoms using the PedsQL[™] Gastrointestinal Symptoms Scales at Month 6, 12
- Change from baseline in Parent Symptoms Score Questionnaire at Month 6, 12
- Parent Symptoms Score Questionnaire at Month 6, 12
- Parent Global Impression Score at Month 6, 12
- Clinical Global Impression Improvement Scale at Month 6, 12
- Incidence and change from baseline in abnormalities in standard awake 45-minutes-EEG monitoring at Month 6, 12

All of the above secondary efficacy endpoints will be presented by listings only.

• Determination of vector shedding analysis in plasma, saliva, urine and feces will provide preliminary data for the ERA

Vector shedding samples will continue to be collected and analyzed until two consecutive negative samples are collected or completion of the study by the subject, whichever comes first.

Observed values and change from baseline in copies per 1mL of specimen in plasma, saliva, urine and feces will be summarized descriptively at baseline and each post-baseline time point. Copies per 1mL of specimen in feces will be presented as a spaghetti plot over each visit by subject.

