5.5.2.5. Day 60 (+/- 7 days)

The following evaluations will be conducted at Day 60:

- Medical history
- Adverse events
- Concomitant medications
- Physical examination
- Vital signs (temperature, heart rate, respiratory rate, blood pressure)
- Weight
 - Labs will be obtained, including: AST, ALT, serum/plasma GGT
 - Plasma and leukocyte SGSH enzyme activity levels
 - Plasma heparan sulfate levels

- Troponin
- Urine GAG and heparan sulfate levels
- ELISpots for T-cell responses to AAV9 and SGSH
- ELISA for detection of total antibodies to AAV9 and antibodies to SGSH
- CCI
- Plasma biobanking
- Amylase (if applicable)
- Samples for vector shedding if applicable (plasma, urine, saliva and feces)

Vector shedding analysis post dosing, after Day 30, will be performed on DNA isolated from different biological fluids (plasma, urine, saliva and feces) until two consecutive samples are negative for the presence of viral DNA for each specimen type.

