According to legislation for environmental risk assessments (guidelines EMEA/CHMP/ICH/449035/2009 and EMEA/CHMP/GTWP/125491/2006), shedding is defined as the dissemination of the virus/vector through secreta and/or excreta of the participant. Assessment of the shedding can be utilized to understand the potential risk associated with transmission to third parties and potential risk to the environment. It is worth mentioning that a limited release of the GMO to wastewater is expected after the administration to the participants. Preclinical data in relevant animal model for vector transduction (mice) is showing a positive shedding in feces and urine samples for a period of 35 days with a very low number of vector genomes. Additionally, the pH and biological conditions in urine and feces diminish the potential survival of the genetically modified organism. However, the wastewater is not an ecosystem where GMO can survive for a long period of time. It is expected that GMO will be degraded after administration to humans by endogenous protein and DNA catabolic pathways. Shed vector DNA is expected not to be stable in wastewater. Taking into account these characteristics and the GMO replication incapacity, no interaction of the GMO with the flora, fauna, livestock or migratory species is expected.

The potential GMO release to the environment will be analyzed in serum and biological fluids samples obtained from all treated participants according to the protocol of the clinical trial. As suggested by regulatory guidelines, samples will be taken more frequently in the first days following administration in order to detect a transient shedding profile. Serum, saliva, urine and feces will be collected at Day 0, 1, 2, 7, 14, and 30 after vector administration. Vector shedding analysis will continue to be collected and analyzed until two consecutive negative samples are collected or completion of the study by the participant, whichever comes first. Analysis will be

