3 STUDY OVERVIEW

3.1 Study Design

This Phase I/II clinical trial is an open-label, single dose study of recombinant, selfcomplementary Adeno-Associated Viral Vector (AAV9) carrying the human Nsulfoglucosamine sulfohydrolase (hSGSH) gene under the control of the U1a promoter, scAAV9.U1a.hSGSH, also known as ABO-102, delivered one time intravenously to MPS IIIA participants. The target population includes MPSIIIA participants with a Developmental Quotient (DQ) lower than 60 in middle and advanced phases of the disease that would not be eligible for the clinical trial ABT-001. To ensure that both the middle phase and advanced phase of the disease are adequately represented in the study, a similar number of participants with a cognitive age equivalent of above 18 months (middle) and below 18 months (advanced), as assessed by the Bayley Scales of Infant and Toddler Development, will be enrolled.

During the active phase of the protocol, subjects will have 12 clinic visits and 5 labs visit over a two-year period. However, due to the study early termination, there will be at most 10 clinic visits and 5 lab visits over a one-year period. Unscheduled visits may be needed per the discretion of the investigator. Efficacy and safety will be evaluated.

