5.1 Intent-to-Treat Set (ITT)

The ITT Set will include all enrolled subjects who received ABO-102 and have at least one post-baseline efficacy measurement. Efficacy and safety analyses will be conducted based on the ITT Population.

The primary endpoints, secondary endpoints, **CCI** endpoints will be analyzed using the ITT Set. At the time of the study termination, all 5 enrolled subjects were treated and had at least one post-baseline assessment. Therefore, the ITT Population is equivalent to all patients enrolled and will be used to evaluate both safety and efficacy data and for populating listings.

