8.1.1 Descriptive Statistics

For descriptive statistical summaries, continuous variables will be summarized by number of observations (n), mean, standard deviation (SD), standard error (SE), median, minimum (MIN), and maximum (MAX). For categorical variables, frequency/count and percentage of subjects in each category will be provided.

Minimum and maximum values will be presented at the same precision as the original value. Mean and median values will be rounded to one decimal place greater than the precision of the original value. SDs and SEs will be rounded to two decimal places greater than the precision of the original value. Percentages for summarizing categorical data will be rounded to one decimal place.

The by-subject listings, including data at scheduled and unscheduled visits, will be sorted by subject number, and then by date/time of the records.

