8.1.4 Handling of Missing or Partial Data

- Missing baseline values will not be imputed in any situation.
- Missing post-baseline values for by-visit data will be summarized using the protocoldefined visit windows. If a value is not available within a given window, no imputation will be done.
- If day of birth is missing, the 1st day of the month will be used to calculate chronological age.
- Missing data for AE relationship will be imputed as "Related".
- For incomplete dates for AEs or non-study medications, the missing component(s) will be assumed as the most conservative value(s) possible. Actual data values, as they appear in the clinical database, will be shown in the data listings. Rules for partial dates are described in the table below. If the AE year is missing or AE is ongoing, the end date will not be imputed. Note: in the table, D = day, M = month, and Y = year.

| Parameter | Missing | Additional Conditions | Imputation |
|--------------------|------------|-----------------------------------|----------------------------------|
| Start date for AEs | Time only | | Time will not be imputed; but |
| | | | will be assumed to be after gene |
| | | | transfer time |
| | D only | M and Y same as M and Y of gene | Date of gene transfer |
| | | transfer date | |
| | | M and/or Y not same as M and Y | First day of non-missing month |
| | | of gene transfer date | |
| | D and M | Y same as Y of gene transfer date | Date of gene transfer |
| | | Y not same as Y of gene transfer | Use January 1 of non-missing |
| | | date | year |
| | M, D and Y | None – date completely missing | Date of gene transfer |
| Stop date for AEs | Time only | | Time will not be imputed |
| | D only | | Last day of non-missing month |
| | D and M | | Use December 31 of non- |
| | | | missing year |
| | M, D and Y | Deceased | Date of death |

| Parameter | Missing | Additional Conditions | Imputation |
|------------------|------------|-----------------------------------|--------------------------------|
| | | Not deceased | Date of the end of trial |
| | | | participation |
| Start date for | D only | M and Y same as M and Y of gene | Date of gene transfer |
| concomitant meds | | transfer date | |
| | | M and/or Y not same as M and Y | First day of non-missing month |
| | | of gene transfer date | |
| | D and M | Y same as Y of gene transfer date | Date of gene transfer |
| | | Y not same as Y of gene transfer | Use January 1 of non-missing |
| | | date | year |

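### From Day 60 the shedding summaries drop specimens because they have cleared, so visit means of copies/mL can overstate how long vector persists

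*SAP*

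**What the plan says.** **Sampling.** Protocol section 11 sets a fixed early schedule: "Serum, saliva, urine and feces will be collected at Day 0, 1, 2, 7, 14, and 30 after vector administration". After Day 30, Protocol 5.5.2.5 and footnote 7 of the Schedule of Evaluations continue the analysis only "until two consecutive samples are negative for the presence of viral DNA for each specimen type". SAP 8.2.2 repeats the rule, with completion of the study as the other end point: "Vector shedding samples will continue to be collected and analyzed until two consecutive negative samples are collected".

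**Analysis.** SAP 8.2.2 then plans: "Observed values and change from baseline in copies per 1mL of specimen in plasma, saliva, urine and feces will be summarized descriptively at baseline", and at every post-baseline time point. Under SAP 8.1.1 a descriptive summary of a continuous variable means n, mean, SD, SE, median, minimum and maximum. For absent post-baseline values SAP 8.1.4 says: "If a value is not available within a given window, no imputation will be done". It makes no exception for a specimen that is absent because it cleared. SAP section 10, on changes from the protocol, does not mention the matter.

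**Setting.** SAP 5.1 records that "all 5 enrolled subjects were treated and had at least one post-baseline assessment", and SAP 3.1 that "due to the study early termination, there will be at most 10 clinic visits and 5 lab visits over a one-year period". The scheduled shedding visits after Day 30 that remain are Days 60, 90 and 180 and Month 12.

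**The concern.** Whether a value is present at a late visit depends on the outcome itself. A specimen stops being sampled because it was negative twice, so the values that remain come only from specimens that had not met the rule before that visit. They can include a first or second negative, but never a specimen that has already cleared. A mean over the remainder leans upward and can rise while no child's value is rising.

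The printed n does not repair this. It falls both when a specimen clears and when a subject's participation ends, and this trial was terminated early.

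Shedding is intended as preliminary data for the Environmental Risk Assessment, where the amount and duration of late shedding are what matter. It is also one of the few secondary endpoints in SAP 8.2.2 that gets a summary table; the other endpoints listed there are sent to listings.

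Amylase has a related, weaker problem. Protocol 5.5.2.3 and footnote 10 of the Schedule of Evaluations continue it after Day 30 only while earlier results remain abnormal. If it is tabulated with chemistry by visit under SAP 8.3.2, its late summaries may look more abnormal than the cohort is.

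**Working it through.** The plan states no figure for this point, so there is nothing to reproduce. The size follows from the sampling rule by arithmetic.

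**Inputs from the documents.** There are 5 treated subjects (SAP 5.1) and four specimen types (SAP 8.2.2). Sampling is fixed through Day 30 (Protocol section 11) and then stops per specimen type after two consecutive negatives (Protocol 5.5.2.5). No imputation is done (SAP 8.1.4).

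**Assumption.** A cleared specimen has the value 0 copies/mL. The SAP gives no rule for negative or below-limit results.

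**Ratio.** Let N subjects be in the study at a visit, k of them still sampled for a specimen type, and S the sum of their values. The stopped N − k add nothing to the sum.

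- Observed-only mean = S/k
- All-subject mean = S/N
- Ratio = (S/k) / (S/N) = N/k

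| Subjects in study | k = 4 | k = 3 | k = 2 | k = 1 |
|---|---|---|---|---|
| N = 5 | 1.25 | 1.67 | 2.5 | 5 |
| N = 4 | 1 | 1.33 | 2 | 4 |
| N = 3 | – | 1 | 1.5 | 3 |

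**Assumed example (not trial data).** Five children remain in the study, one specimen type is followed, and no child's value ever rises. Values are copies/mL; a dash means not sampled under the rule.

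| Child | Day 14 | Day 30 | Day 60 | Day 90 | Day 180 | Month 12 |
|---|---|---|---|---|---|---|
| A | 0 | 0 | – | – | – | – |
| B | 200 | 0 | 0 | – | – | – |
| C | 500 | 300 | 0 | 0 | – | – |
| D | 2,000 | 1,000 | 400 | 0 | 0 | – |
| E | 20,000 | 10,000 | 6,000 | 4,000 | 3,000 | 2,500 |

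Through Day 30 both methods agree: 22,700/5 = 4,540 at Day 14 and 11,300/5 = 2,260 at Day 30. After that:

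| | Day 60 | Day 90 | Day 180 | Month 12 |
|---|---|---|---|---|
| Printed n | 4 | 3 | 2 | 1 |
| Printed mean | 6,400/4 = 1,600 | 4,000/3 = 1,333 | 3,000/2 = 1,500 | 2,500/1 = 2,500 |
| All-subject mean | 6,400/5 = 1,280 | 4,000/5 = 800 | 3,000/5 = 600 | 2,500/5 = 500 |
| Printed median | 200 | 0 | 1,500 | 2,500 |
| All-subject median | 0 | 0 | 0 | 0 |
| Positive / in study | 2/5 | 1/5 | 1/5 | 1/5 |

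The printed mean climbs from 1,333 to 2,500 between Day 90 and Month 12, while the only child still shedding falls from 4,000 to 2,500.

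**Reach.** 4 visits × 4 specimen types = 16 visit-by-specimen summaries are exposed. That is a maximum. If nobody has cleared a specimen, the ratio is 1. If everybody has cleared before the visit, n is 0 and no mean is printed.

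**The case against.** The strongest reply is that little depends on the table. The endpoint is descriptive, there are 5 subjects and no test, all collected data are listed by subject and date (SAP 8.1 and 8.1.1), and feces has a by-subject plot. Disposition with reasons (SAP 7.1) and study duration categories (SAP 7.6) help to separate clearance from end of participation. The error also runs in the cautious direction for an environmental assessment. All of this is true and keeps the point from being critical. But the reader must assemble several outputs to undo what the table shows, and plasma, saliva and urine have no planned plot.

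A second reply concerns the wording of the rule. SAP 8.2.2 does not say that it applies per specimen type, and Protocol section 11 in one place speaks of the participant showing two negatives. If every type continued until all had cleared, the distortion would shrink. If only samples after Day 30 counted towards the two negatives, the first omission would come at Day 180, leaving 2 visits × 4 types = 8 summaries exposed. However, footnote 7 and Protocol 5.5.2.5 name each specimen type, and Day 60 samples are already conditional. Under any of these readings the table can still lose cleared specimens.

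Third, counting stopped specimens as negative is itself a form of imputation. It is, but it assumes no more than the sampling rule does when it stops looking. A count of positives also needs no invented copies/mL value. The amylase part is conditional on how the SAP's chemistry tables are built and carries no calculation, so it should be read as secondary.

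**Conclusion.** The concern holds. Followed as written, the plan removes cleared specimens from the shedding summaries at Days 60, 90 and 180 and Month 12, and it can overstate persistence there. Bias arises at a visit when at least one subject still in the study has cleared the specimen type and at least one still sheds. With cleared values taken as 0, the mean is then too high by N/k, which for 5 subjects is between 1.25 and 5 times. How many subjects clear, and when, is not in the documents, so the actual size cannot be stated. Summaries through Day 30 are sound, and no error rate or sample size is affected. The change is recommended because the table serves the environmental risk assessment and the remedy is cheap.

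**What to change.** In SAP 8.2.2, as an explicit exception to 8.1.4:

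- State that a subject's specimen type stopped under the two-negatives rule counts as negative (below detection) at later scheduled visits, up to the end of that subject's participation.
- For each specimen type and visit, report the number positive out of subjects still in the study.
- Beside n for any mean of observed values, show the number stopped for clearance.
- For amylase after Day 30, list individual values and omit the by-visit mean.

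Optional additions are time to the first of two consecutive negatives, and by-subject plots for plasma, saliva and urine.

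The cost is a short SAP paragraph, one count table per specimen type and one extra column; no new data are needed. The downside is small: the counts assume that vector does not reappear after two negatives, which the sampling rule already presumes.

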8.3 Safety Analyses

8.3.1 Adverse Events (AEs)

AE tables (except for AE overview table) will only include summaries of treatment-emergent adverse events (TEAE). TEAEs will be defined as those occurring during or after gene transfer on Visit 3 (Day 0). All AEs should be reviewed by Medical Monitor or Designee before the database is locked. All reported terms (investigator descriptions) for AEs should be reviewed by Medical Monitor or Designee before the database locked and will be coded using the latest version of MedDRA. Number and percentage of subjects with TEAEs will be summarized by system organ classification and preferred term.

An overview table will be provided with the number and percent of the following categories, if applicable:

- Number of total AEs, TEAEs, and deaths
- Incidence of patients with at least one: TEAE, TEAEs related to study treatment (IMP-related TEAE), SAE, IMP-related SAE, non-serious TEAEs, and deaths
- Incidence of patients who discontinued due to: TEAE, IMP-related TEAE, SAE, and IMP-related SAE
- Incidence of deaths and deaths due to IMP-related TEAE

TEAEs leading to discontinuation of study drug, IMP-related TEAE, serious TEAEs, nonserious TEAEs, and TEAEs by severity will be summarized and listed. Deaths will be listed, if any.

AEs occurring prior to gene transfer are defined as pre-treatment AEs and will be listed only.

AEs with relationship 'Possible', 'Probable', or 'Definitely' to IMP are defined as AEs related to study treatment.

Safety primary endpoint

• Product Safety as defined by the incidence, type and severity of treatment-related AEs and SAEs at Month 1, 2, 3, 6, 12

Product safety will be assessed by the incidences of treatment-related AEs and SAEs type and severity at each time point (<1 month, 1-<2 months, 2-< 3 months, 3-<6 months, 6-<12months, and >= 12 months from treatment date to AE onset date). Counts of subjects and percentages will be provided for baseline and post-baseline visits. Treatment-related AE is defined as AE that is 'Possible', 'Probable' or 'Definitely' related to study drug.

8.3.2 Clinical Laboratory Evaluations

Hematologic, chemistry, coagulation and urinalysis laboratory measurements will be summarized by visit. For the continuous data, descriptive statistics (n, mean, SD, median, minimum, maximum) in change (absolute and percent) will be presented. For the categorical data, the number and the percentage of subjects for each observed category under each analyte will be summarized.

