6. Plasma, urine, feces and saliva vector shedding samples collected at 4- and 8-hours post gene transfer.
7. Vector shedding analysis post dosing will be performed on DNA isolated from different biological fluids (plasma, urine, saliva and feces) until two consecutive samples are negative for the presence of viral DNA for each specimen type.

8. To be performed if not previously documented.
9. CCI of the injection site to be taken prior to and after (approximately 24 h after infusion) vector administration.
10. Further analysis only to be performed if previous results remain abnormal.
11. Kaufman Battery will be used together with or replacing to the Mullen and/or Bayley scales based on developmental age results obtained with those scales.
12. Neurocognitive Validity Form part 1 for Bayley Scales Infant and Toddler Development/Kaufman Battery and Vineland Adaptive Behavior Scale II- Survey form.
13. Neurocognitive Validity Form part 2 for Mullen Scales of Early Learning, CCI PSI-4, PedsQL, and CSHQ if applicable.

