5. STUDY PROCEDURES

5.1. Schedule of Evaluations

This clinical trial protocol is based in large part on observations from MPS IIIA and MPS IIIB participants enrolled in the observational study previously described, and the ABT-001 clinical trial which is currently ongoing (NCT02716246, EudraCT number 2015-003904-21).

Additionally, according to local regulatory requirements, a plan for vector shedding in blood and other body fluids is included as part of an environmental risk assessment.

For a general overview of the procedure and visits, please see the [Schedule of Evaluations](#).

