5.5.2.3. Day 30 (+/- 3 days)

The following evaluations will be conducted at Day 30:

- Medical history
- Adverse events
- Concomitant medications
- Physical examination
- Vital signs (temperature, heart rate, respiratory rate, blood pressure)
- Height and weight
- Abdominal MRI to measure liver and spleen volumes
- Labs will be obtained, including
 - CBC and differential
 - Electrolytes
 - Serum/plasma total protein
 - Albumin
 - PT, PTT, INR
 - Creatinine/BUN
 - AST, ALT, serum/plasma GGT
 - Alkaline phosphatase
 - Amylase
 - Serum/plasma total bilirubin
 - Random glucose
 - Troponin
 - Plasma and leukocyte SGSH enzyme activity levels
 - Plasma heparan sulfate levels
 - Urine GAG and heparan sulfate levels

- Urinalysis
- ELISpots for T-cell responses to AAV9 and SGSH
- ELISA for detection of total antibodies to AAV9 and antibodies to SGSH
- CCI
- Plasma biobanking
- Lumbar puncture (LP) will be performed under sedation/anesthesia
 - CSF analysis
 - SGSH enzyme activity
 - heparan sulfate levels
 - CCI
 - Protein, glucose, cell count and differential
 - CCI
 - CSF biobanking
- Samples for vector shedding (plasma, urine, saliva and feces)

If an elevation in amylase levels is observed after gene transfer and has not returned to baseline values by Day 30, amylase will continue to be analyzed in further visits until levels return to baseline values. Those analyses will include lab collections performed at home if the participant is unable to travel to the hospital.

5.5.2.4. 5.5.2.4 Day 45 (+/- 3 days)

Lab work at Day 45 will be done to evaluate safety. Participants unable to travel to the hospital will have their blood drawn by a contracted home care service.

The labs will evaluate:

- ○ AST, ALT, serum/plasma GGT

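### By-visit mean amylase change after Day 30 (SAP 8.3.2) describes mainly children whose elevation has not resolved, so it can overstate the change in the 5 treated

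*SAP*

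**What the plan says.** SAP 8.3.2 sets one rule for all laboratory data: "Hematologic, chemistry, coagulation and urinalysis laboratory measurements will be summarized by visit". For continuous data, "descriptive statistics (n, mean, SD, median, minimum, maximum) in change (absolute and percent) will be presented". It does not name amylase, but amylase is a scheduled blood test that falls naturally under chemistry, and the SAP gives no exception or separate summary for it. On missing visit values SAP 8.1.4 says: "If a value is not available within a given window, no imputation will be done".

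The protocol schedules amylase for every child at screening, Day -1 and Days 1, 7, 14 and 30. From Day 45, each amylase entry in the Schedule of Evaluations carries footnote 10: "Further analysis only to be performed if previous results remain abnormal". Section 5.5.2.3 gives the fuller rule. The trigger is: "If an elevation in amylase levels is observed after gene transfer and has not returned to baseline values by Day 30". In that case "amylase will continue to be analyzed in further visits until levels return to baseline values", with home draws where travel is not possible. The Day 60 and Day 90 lists mark amylase as conditional.

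**The concern.** After Day 30, whether a child has an amylase value depends on that child's earlier amylase results. Children whose level is back at baseline leave the denominator, and the mean is then taken over those who remain. Because nothing is imputed, a row for Day 45 or later covers mainly children who were unresolved at their previous measurement, including the value at which each is first found to have resolved.

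Reading down the table, a clinician could see mean change hold steady or rise when the children's values are falling. Protocol section 6 names amylase among the analytes that deserve special attention, so this row is likely to be read. The printed n shows that values are absent but not why. A small n could be taken for missed visits when it reflects recovery.

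**Working it through.** The plan gives no figure for amylase, so there is nothing to reproduce. Two things can be checked: how much of the schedule is conditional, and what conditional sampling does to a mean over 5 children.

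**Schedule.** Post-dose amylase columns through Month 12 (the truncated follow-up in SAP 3.1):
- Unconditional: Days 1, 7, 14, 30 = 4.
- Under footnote 10: Days 45, 60, 75, 90, two weeks after steroids, Days 120, 150, 180, Month 12 = 9.
- Share conditional: 9 / (4 + 9) = 9/13 = 69%.

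This counts columns where selection can operate. It does not count rows known to be affected.

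**Arithmetic (illustrative).** Five children were treated (SAP 5.1). Assume that k of them are above baseline at Day 30 with mean rise C, that the other 5 - k are at 0, and that only the k are sampled at Day 45, when a fraction r of C remains on average.
- Day 30 mean, n=5: kC/5.
- Day 45 tabulated mean, n=k: rC.
- Day 45 mean over all five: rkC/5.
- Tabulated over five-child mean: 5/k.
- The tabulated mean rises from Day 30 to Day 45 if rC > kC/5, that is, if r > k/5.

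| k | 5/k | Tabulated mean rises unless the average elevation has fallen by at least |
|---|---|---|
| 1 | 5.00 | 80% |
| 2 | 2.50 | 60% |
| 3 | 1.67 | 40% |
| 4 | 1.25 | 20% |
| 5 | 1.00 | no distortion |

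With k=0 the later cells are empty unless extra samples are taken.

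Invented examples with C = +100% and r = 0.6:
- k=1: tabulated +20% to +60%; all five +20% to +12%.
- k=2: tabulated +40% to +60%; all five +40% to +24%.
- k=1 with the other four at -10%: tabulated +12% to +60%; all five +12% to +4%.

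**Dilution.** Protocol section 5.2 lets the investigator order extra analyses, so some resolved children may also have values. With m of them sampled at 0, the tabulated mean is rkC/(k+m). For k=1 this is +60%, +30%, +20%, +15% and +12% for m = 0 to 4.

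**Simulation (all amylase values assumed).** Groups of 5, 40,000 replicates, pre-dose level 60 U/L, within-child SD 8, median peak rise 60 U/L, sampling stopped once within 10% of baseline. Mean change at Day 90, tabulated (over replicates with at least one child sampled) against all five:
- median half-life 15 days: 13.5 vs 3.6 U/L;
- 30 days: 22.1 vs 13.4 U/L;
- 60 days: 35.5 vs 29.4 U/L.

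At Day 30 the two means agree. In these runs the average tabulated mean still fell from Day 30 to Day 45 (43.8 to 34.5 U/L at 30 days) but stayed above the five-child mean (31.6 U/L). Overstatement is therefore the general effect, and an apparent rise is a possible special case.

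**The case against.** The best defence is that the plan already shows what a reader needs. SAP 8.3.2 prints n, minimum and maximum beside each mean, and SAP 8.1 lists all data. A row with n=1 has identical mean, median, minimum and maximum and no SD, so it can hardly pass for a five-child mean. Mean amylase feeds no endpoint, test or stopping rule. The request in protocol section 6 for special attention to amylase sits with the recording of clinically significant laboratory findings as adverse events, and SAP 8.3.1 analyses those per child. All of this stands, and it makes the point minor. It does not tell a reader that values are absent because the elevation resolved, which is less obvious at n=2 to 4.

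It is also fair that the five-child mean above rests on unsampled children staying near baseline, which nobody measured. If they later rose as high as those still sampled, the overstatement would vanish.

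A reader might infer that the protocol holds two conflicting continuation rules, because footnote 10 speaks of abnormal results and section 5.5.2.3 of return to baseline. The documents do not support making this a defect. Section 5.1 offers the schedule only as an overview ("For a general overview of the procedure and visits, please see the" schedule), section 5.5.2.3 is the fuller rule, and the footnote can be read as shorthand for it. With all 5 children already treated, rewording it would change little.

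**Conclusion.** The point holds as a minor improvement to a descriptive table. The selection follows from the written rules: conditional sampling after Day 30, by-visit means without exception, no imputation. Overstatement follows if between 1 and 4 of the 5 children remain elevated at Day 30 and the unsampled ones stay nearer baseline than those sampled.

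The size cannot be given. A reader might infer that the late amylase rows will be badly wrong, or that the safety conclusion is at risk. The documents support neither: they report no amylase values and do not say that any child was elevated at Day 30. The percentages and U/L figures show direction and possible range only.

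**What to change.** In SAP 8.3.2, add two sentences. First, limit the by-visit summary of amylase change to visits through Day 30. Second, for later visits, report the number of children still being followed for an unresolved post-dose elevation out of the 5 treated, applying the rule in protocol section 5.5.2.3. Show each child's individual values and the last measured value with its date, and impute nothing for unsampled children.

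The cost is two sentences and the loss of a late mean; every value remains in the listings. Return to a single pre-dose value is a strict criterion, so small above-baseline variation may count as unresolved. The individual values should therefore stand beside the count.
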